## 6.0 STUDY OBJECTIVES AND ENDPOINTS

Objectives	Endpoints
Primary To determine the performance characteristics of oral lollipop swabs compared to NP swabs for diagnosing COVID-19 via PCR molecular testing.	Tabulated results from NP vs. lollipop swab-based PCR COVID-19 tests.
Secondary To identify clinical characteristics of patients when there are discordant results for NP and oral lollipop test results.	Correlation of clinical characteristics to participants with discordant test results

## 7.0 STUDY DESIGN

### 7.1 General Design

The Inpatient COVID-19 Lollipop Study is a prospective, single-center study to determine if oral lollipop swabs provide an adequate/optimum sample for diagnosing COVID-19. A total of up to 225 COVID-positive inpatients ages 4 years and older will be enrolled at one study sites. Subject accrual will occur over 6 months with the total duration of the study expected to be 12 months.

Eligible subjects will complete 1 visit that will last approximately 30 minutes. After the study team obtains informed consent and assent, if applicable, the study team will provide verbal instructions and supervise participants as they suck on a flocked swab for 20 seconds. The sample will be labeled with the study ID code and date of sample acquisition, and the result (positive or negative) of the lollipop swab will be compared to the NP swab results in the participant's medical record. Clinical information including symptoms, duration of symptoms, known past COVID-19 infections, known COVID-19 household contacts within 90 days, and COVID-19 immunization status will be assessed via conversation with the participant and review of the electronic medical record. Laboratory information including the cycle threshold of the NP sample will be collected. Each participant will be classified as having either symptomatic or asymptomatic infection. The electronic medical record will be reviewed for medical record number, birthdate, and the above clinical information regarding COVID-19. The sample will be sent to the Wisconsin Veterinary Diagnostic Lab (WVDL) for performance of the PCR for SARS-CoV-2. The specimens will be discarded in the lab after the sample has been processed.

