### 3.2 Schematic of Study Design

Prior to Enrollment

Screen potential participants by inclusion and exclusion criteria. Conduct consenting process and obtain informed consent.

Visit 1  
Time Point

Confirm and document eligibility. Administer verbal questionnaire to collect clinical and demographic information. Supervise lollipop method of collecting a saliva sample.

Post-Visit

Collect information from participant's electronic medical record and enter into the research database.

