### **10.3.1 Study Visit**

Study visits will occur in a private location, such as the participant’s hospital room, during their inpatient stay at AFCH or University Hospital. Study team members will adhere to the University Hospital’s personal protective equipment (PPE) requirements. After verbal consent/assent is collected and documented in REDCap, the study team will collect basic information about participants, including their name, date of birth, sex, race and ethnicity. If participants are younger than 18 years old, the study team will collect their parent or guardian’s name. The study team will also collect information from participants or their parent/legal guardian verbally and from the participant’s medical record. The information will be relevant to their COVID-19 symptoms and diagnosis, as well as their vaccination status. A detailed list of data points can be found in the Data Collection Sheet. The study team will record this information directly in the study’s SMPH REDCap project. Once a study team member has collected this information, they will guide the participant through the lollipop swab collection. The lollipop swab is obtained by sucking on a swab for 20 seconds in the same way that one would suck on a lollipop. The study procedures will take approximately 15-30 minutes to complete.

A study team member will transport the lollipop swab to the WVDL as soon as possible. The WVDL will provide the study team with the COVID-19 PCR results.

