## **12.0 STUDY ANALYSIS**

### **12.1 Statistical Hypotheses**

- Primary Efficacy Endpoint(s):**

- For participants who have had COVID-19 symptoms for <5 days, the sensitivity of lollipop swab-based PCR COVID-19 testing is non-inferior to the sensitivity of NP swab-based PCR COVID-19 testing.

- Secondary Efficacy Endpoint(s):**

- For participants who have had COVID-19 symptoms for  $\geq 5$  days, the sensitivity of lollipop swab-based PCR testing is inferior by 50% to the sensitivity of NP swab-based PCR COVID-19 testing.
- For participants who are asymptomatic, the sensitivity of lollipop swab-based PCR testing is inferior by 50% to the sensitivity of NP swab-based PCR COVID-19 testing.

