### **12.4 Statistical Methods**

Sensitivity and specificity of the lollipop swabs will be calculated.

The primary variable is binary (positive or negative). A separate subgroup analysis of sensitivity/specificity of lollipop swabs will be calculated for asymptomatic, symptomatic (<7 days), and symptomatic (>7 days) individuals.

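### The symptom group that defines the 12.1 hypotheses is not fixed before the lollipop result is known, and no swab is named as the end of the symptom clock

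*Combined protocol and SAP*

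**What the plan says.** The primary hypothesis in section 12.1 is limited by symptom duration: "For participants who have had COVID-19 symptoms for <5 days, the sensitivity of lollipop swab-based PCR COVID-19 testing is non-inferior" to that of NP testing. Participants with 5 or more days of symptoms, and those without symptoms, have separate secondary hypotheses, each of sensitivity inferior by 50%.

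Section 7.1 describes how the groups arise. Symptoms and their duration "will be assessed via conversation with the participant and review of the electronic medical record", and then: "Each participant will be classified as having either symptomatic or asymptomatic infection". It names no qualifying symptoms, no assessor, no time point and no rule for an interview and a chart that disagree.

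On timing, three places bear on the question:
- Section 10.3.1 has symptom information gathered from the participant and the medical record, entered in REDCap, and only then the lollipop swab taken. It adds: "The WVDL will provide the study team with the COVID-19 PCR results".
- The post-visit step of the section 3.2 schematic reads: "Collect information from participant's electronic medical record and enter into the research database".
- The section 10.1 calendar marks medical-record collection under the post-study visit column only.

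Section 8.1 allows the lollipop swab up to 48 hours after the diagnostic NP swab. Section 12.4 uses a different set of strata: "asymptomatic, symptomatic (<7 days), and symptomatic (>7 days) individuals".

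**The concern.** A participant's symptom group decides whether a negative lollipop counts against the primary hypothesis or falls under a secondary hypothesis that expects lower sensitivity. A variable with that role should be fixed without knowledge of the test result and by one stated clock. The plan secures neither.

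The two gaps act differently. If the group is settled or amended once the result is known, the error can be related to the outcome, and subgroup sensitivity can be biased in either direction. If the clock has no stated end, the error is not tied to the result. It mixes early and late participants and so mainly blurs the difference between groups that section 12.1 sets out to test.

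**Working it through.** **Plan's own figure.** Section 12.2 gives 206 from 88%, 80%, 5% type I error and 90% power, without naming a method. A two-sided one-sample test of a proportion reproduces it: n = [(1.960·√(0.88×0.12) + 1.2816·√(0.80×0.20)) / 0.08]² = [(0.6369 + 0.5126) / 0.08]² = 206.5. This point does not dispute or change that number.

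**Step 1: when the group can be set.** Read together, the sections give this order: interview and chart data into REDCap (10.3.1), lollipop swab (10.3.1), then further chart collection (3.2, 10.1) and return of the result to the team (10.3.1). No section places the classification in that order, masks whoever makes it, or freezes it. Section 10.3.1 also differs from 3.2 and 10.1 on whether the chart is read before the swab or after the visit.

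**Step 2: the clock.** Let d be days of symptoms at the NP swab and g the gap to the lollipop swab, at most 2 days. A participant changes group when d < 5 and d + g ≥ 5.
- At g = 2, this is every d from 3 to <5, or 2 of the 5 days in the primary window.
- At g = 1, it is every d from 4 to <5, or 1 of the 5 days.

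These are shares of the window, not of participants. They become 40% and 20% of the early group only if symptom days are evenly spread and everyone has that same gap; 48 hours is the maximum. A participant without symptoms at the NP swab may also have them by the lollipop swab. Under the 7-day cut in 12.4 the same problem arises for d from 5 to <7.

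**Step 3: effect of errors unrelated to the result.** Assume a true early-group sensitivity of 0.88 (the pilot figure) and a fraction f of that group misplaced from elsewhere. Observed sensitivity = (1 − f)×0.88 + f×s.
- With s = 0.44 (half of 0.88): f = 10% gives 0.836 and f = 20% gives 0.792.
- With s = 0.50 (half of an NP sensitivity that is 100% by the entry criterion): f = 10% gives 0.842 and f = 20% gives 0.804.

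The early-group estimate falls towards the others. It would take f = 0.08/0.44 = 18%, or 0.08/0.38 = 21%, to lower it by the 8 points that separate 88% from 80%.

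**Step 4: effect of changes made with the result known.** Assume 100 in the early group, 80 positive and 20 negative.
- 5 negatives moved out: 80/95 = 84.2%.
- 10 negatives moved out: 80/90 = 88.9%.
- 5 positives moved out: 75/95 = 78.9%.
- 5 negatives moved in: 80/105 = 76.2%.

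The size depends on the assumed group. With 20% negative and 5 negatives moved out, a group of 60 goes from 80.0% to 48/55 = 87.3%, and a group of 150 from 80.0% to 120/145 = 82.8%.

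**Step 5: whole cohort.** Overall sensitivity is lollipop positives divided by all NP-positive participants with a result. Symptom group does not enter it, so no relabelling can move it.

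**The case against.** The strongest reply is that section 10.3.1 already collects symptom data, from interview and chart, before the specimen exists. That stands, and it limits the exposure to the final classification and to chart data added later. It does not close the gap, because 3.2 and 10.1 put chart collection after the visit and no section says when the group is fixed.

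Section 10.3.1 also refers to a Data Collection Sheet that is not in the documents and may define symptoms or ask for an onset date. That is fair, so it cannot be said that the grouping is left to judgement. Even so, the clock and the lock define a hypothesis population and belong in the protocol.

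It can be argued that duration asked about at the bedside naturally means duration at the lollipop visit. This is a reasonable reading, but it is nowhere written.

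The role of the early group is itself less settled than 12.1 suggests. The primary objective and endpoint (6.0), the analysis population (12.3) and the opening analysis in 12.4 are not restricted by symptoms. This also stands.

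A reader might infer that the team will classify after seeing results and that the primary estimate will be inflated. The documents do not support that. They do not say who classifies or when, and they describe no result-driven relabelling. Section 12.1 predicts inferiority by 50% in the other groups, not uniformly negative swabs, so the pull towards relabelling negatives is weaker than it may first appear.

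**Conclusion.** The point holds as an avoidable opening for bias, not as evidence of bias. The plan does not fix the symptom group before the lollipop result and does not say which swab ends the symptom clock. The first gap could bias subgroup sensitivity in either direction; the second would mainly dilute the contrast between groups.

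No firm size can be given, since the documents state neither group sizes nor misclassification rates. The shift from 80.0% to 84.2% rests on an assumed group of 100 and five negatives moved in one direction. The dilution figures rest on assumed sensitivities and misplaced fractions. Whole-cohort sensitivity and the sample size of 206 are untouched. The change is worth making because it is cheap and protects the groups on which all three hypotheses in 12.1 depend.

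**What to change.** In sections 7.1 and 10.3.1:
- Record the symptom-onset date, or 'no COVID-19 symptoms', in REDCap before the swab is taken, in the order that 10.3.1 already sets.
- Count duration to the date and time of lollipop collection.
- Lock the group before the WVDL result is entered.

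In section 12.4:
- Use the locked, pre-result classification for the primary analysis.
- Log and count any later chart-based change and use it only in a sensitivity analysis. No separate masked assessor is then needed.
- Add a sensitivity analysis with duration counted to the NP swab.

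Reconcile 10.3.1 with 3.2 and 10.1 on when the chart is read, and 12.1 with 12.4 on the 5-day versus 7-day cut; as written, 12.4 also leaves out exactly 7 days.

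The cost is a REDCap lock with a log of changes and one extra table covering the sensitivity analyses. No additional participants, visits or samples are needed.

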## 7.2 End of Study Definition

The end of the study is defined as the date of completion of any final follow-up activity or data collection described in the protocol.

# 8.0 SUBJECT SELECTION

## 8.1 Inclusion & Exclusion Criteria

Eligibility will be determined by inclusion and exclusion criteria below and confirmed by medical record review as necessary.

### Inclusion Criteria

1. Ability to understand and the willingness to provide verbal informed consent, if 18 years or older. If 4-17 years old, ability to understand and the willingness to provide verbal assent, plus have a parent or legal guardian present who can provide verbal informed consent.
2. Willing to comply with all study procedures and be available for the duration of the study.
3. Admitted to UW Health University Hospital or UW Health Kids American Family Children's Hospital.
4. Individuals at least 4 years of age.
5. Verified COVID-19 according to positive NP PCR test criteria.
6. Enroll within 47 hours of the diagnostic NP swab; lollipop swab collected within 48 hours of the diagnostic NP swab.
7. Either personally able or have a parent or legal guardian able to verbally answer questions in English about clinical symptoms, exposures, and other health and demographic information.

### Exclusion Criteria

1. Unable to suck on a swab.
2. Previous participation in this study.
3. Require translation services for medical care.
4. Not suitable for study participation due to other reasons at the discretion of the investigators or their designee.

## 8.2 Vulnerable Populations

This study will enroll children because the research is critical to advance the care of children with COVID-19. The study presents minimal risk to children, as there are no known or anticipated risks of the lollipop

swab collection method. Confidentiality risks are minimal, as this study does not involve collection of sensitive data. The research will help inform an important scientific question that may benefit children in the future. To further minimize risks to children, permission will be obtained from a single parent/guardian, and verbal assent will be obtained using age-appropriate language. Child dissent will always be respected.

This study will enroll pregnant persons because the diagnostic testing method being studied will present no more than minimal risk to the fetus, as the study procedures involve the pregnant subject, who is already known to be COVID-positive, sucking on a sterile swab and verbally answering questions. This study will not seek to identify the pregnancy status of subjects. Pregnant women may be enrolled, but pregnancy status will not be identified as part of study procedures or included in research records.

### **8.3 Lifestyle Considerations**

During this study, subjects are asked to:

- Always wear a face mask, except when they are collecting the saliva sample.
- Refrain from eating or drinking directly before collecting the saliva sample.

### **8.4 Subject Identification**

#### **8.4.1 Best Practice Alerts**

The study team will set up Best Practice Alerts in Health Link so they are notified when a potentially eligible patient is admitted for inpatient care at UW Health.

#### **8.4.2 Identification in Clinical Practice**

Potential subjects may be identified by study team members who provide clinical care to patients with COVID-19. A member of the clinical team will inform potential subjects of the research opportunity and provide an IRB-approved study flyer. Potential subjects will be pre-screened through medical record review. Potential subjects who meet all eligibility criteria will be invited to enroll in the study.

#### **8.4.3 Reporting Workbench**

Study staff with UW Health electronic health record (Health Link) access may search patient list templates made available to them as part of their research access to Health Link to help identify potential subjects for study enrollment evaluation.

### **8.5 Subject Recruitment**

A total of 225 subjects will be recruited from 1 site in the United States. Individuals from populations who are underrepresented in clinical research (e.g., racial and ethnic minorities, women, individuals from rural and underserved communities, older individuals, federally recognized nations and tribes) will be enrolled with a goal of ensuring that all eligible patients are given the opportunity to participate in novel clinical trials and that research findings can be generalizable to the entire population.

Several recruitment strategies will be employed, and the study team will use a combination of methods. Specific recruitment strategies are as follows:

#### **8.5.1 Recruitment through Clinical Practice**

If the potential subject is agreeable, they will be provided a flyer and contact information for the study team or the research team will initiate contact.

#### **8.5.2 Posters/Flyers**

Flyers announcing that volunteers are needed for a study may be posted in UW Health Inpatient settings, as well as waiting rooms. Several key details of the study will be included in the flyer (key eligibility criteria, number and length of visits, location of study site, type of remuneration) along with a call back number for people to call in case they are interested.

## 8.6 Remuneration and Retention Strategies

Strategies for retention include:

- Streamline data and sample collection to make the study visit as short as possible, approximately 30 minutes.

## 8.7 Early Termination and Withdrawal

Subjects are free to withdraw from participation in the study at any time upon request.

The Principal Investigator (PI) may discontinue or withdraw a subject from the study for the following reasons at his/her discretion:

- Subject non-compliance with study requirements (e.g., unwilling or unable to suck on swab)
- If any clinical adverse event (AE), laboratory abnormality, or other medical condition or situation occurs such that continued participation in the study would not be in the best interest of the subject
- If the subject is no longer an appropriate candidate for participation

Subjects who provide verbal informed consent/assent but do not provide a lollipop swab that can be successfully resulted will not be replaced. Subjects who provide verbal informed consent/assent and provide a lollipop swab that can be successfully resulted, then subsequently withdraw, or are withdrawn or discontinued from the study, will not be replaced.

The study team will attempt to obtain the following information from subjects following early termination or withdrawal: self-reported reason for withdrawal.

## 9.0 STUDY AGENT (STUDY DRUG, DEVICE, BIOLOGIC, VACCINE, ETC.) AND/OR PROCEDURAL INTERVENTION AND/OR BEHAVIORAL/SOCIAL INTERVENTION

### 9.1 Study Agent and Control Description

#### Investigational Devices

Both the “lollipop” collection swab and the lollipop swab processing procedure qualify as an exempt diagnostic device/test based on the Code of Federal Regulations device exemption guidelines. The swab and test are non-invasive, do not introduce energy to a subject, do not require invasive sampling, and are not used as a diagnostic procedure without confirmation of the diagnosis by another medically established test. Neither the swab nor the test meet the definition of “significant risk,” which is a device that presents a potential for serious risk to health, safety or welfare of subjects.

#### 9.1.1 Source

The study team is already in possession of a supply of flocked swabs. The swabs are consistent with the type of swabs used for standard-of-care NP swabs.

#### 9.1.2 Packaging and Labeling

The study team will add labels to each packaged swab with the statement "CAUTION - Investigational Device. Limited by Federal (or United States) Law to Investigational Use." [§ 812.5(a))].

#### 9.1.3 Preparation

##### 9.1.3.1 Investigational Swab

A study team member will open the package of the swab and offer the end of the stick to the participant, instructing them to only touch the other end of the stick (i.e., the flocked end of the swab) to the inside of their mouth and nowhere else.

#### 9.1.3.2 Investigational Assay

The COVID-19 PCR assay will be prepared and performed by the Wisconsin Veterinary Diagnostic Lab (WVDL), in the same way that samples are processed for standard of care.

### 9.1.4 Storage and Stability

Prior to use, the swabs must be stored separately from normal hospital stocks and must be stored in a securely locked area accessible only to authorized study personnel until used. Approved study team members will store, handle, and guide administration of the devices. If the package of a swab is damaged such that it is no longer sterile, the swab will be discarded.

#### 9.1.4.1 Swab Handling After Saliva Collection

The swab will be taken to the Wisconsin Veterinary Diagnostic Lab as soon as possible. If it cannot be delivered to the lab on the same day as collection, then it may be temporarily stored in a designated refrigerator or freezer.

### 9.1.5 Accountability

The study team is already in possession of all swabs that will be used for the study.

### 9.1.6 Administration

A study team member will instruct the participant to suck on the swab for 20 seconds in the same way that they would suck on a lollipop.

## 9.2 Method for Assigning to Treatment Groups

Not applicable.

## 9.3 Study Intervention Compliance

Immediately after each study visit, the study team member will complete a Reportable Event Form that asks about protocol deviations, adverse events, participant complaints, and/or any other potentially reportable events that may have occurred. A participant's data will be included in analyses if their lollipop saliva sample is successfully resulted.

## 9.4 Concomitant Therapy

### 9.4.1 Permitted Concomitant Therapy

All concomitant therapies are permitted.

### 9.4.2 Prohibited Concomitant Therapy

No concomitant therapies are prohibited.

## 10.0 STUDY VISITS AND PROCEDURES

### 10.1 Study Calendar

The procedures performed at the single study visit are listed in the table below.

Procedure	Study Visit	Post-Study Visit	End of Study/Early Withdrawal
Informed Consent/Accent	X		
Demographic and Health Verbal Questionnaire	X		
Lollipop Swab Saliva Collection	X		
Adverse Event Review and Evaluation			X
Collect Information from Medical Record		X	

